### 5.3.2.2. Exposure

No imputation will be done for first dose date. Date of last dose of study drug, if unknown or partially unknown, will be imputed as follows:

- If the last date of study drug is completely missing and there is no End of Treatment eCRF page and no death date, the participant should be considered to be ongoing and use the cutoff date for the analysis as the last dosing date.
- If the last date of study drug is completely or partially missing and there is EITHER an End of Treatment eCRF page OR a death date available (within the data cutoff date), then impute this date as the last dose date:
  - = 31DECYYYY, if only Year is available and Year < Year of min (EOT date, death date)
  - = Last day of the month, if both Year and Month are available and Year = Year of min (EOT date, death date) and Month < Month of min (EOT date, death date)
  - = min (EOT date, death date), for all other cases.

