## 2. INTRODUCTION

This SAP provides the detailed methodology for summary and statistical analyses of the data collected in Study B8011006. This document may modify the plans outlined in the protocol; however, any major modifications of the primary endpoint definition or its analysis will also be reflected in a protocol amendment.

A separate SAP will cover the periodic safety review by the External Data Monitoring Committee (E-DMC).

Statistical analyses will be performed using cleaned electronic case report form (eCRF) data as well as non-CRF data (i.e., PRO, pharmacokinetic (PK) concentration, anti-drug antibody (ADA), neutralizing antibody (Nab), biomarker data, and Blinded Independent Central Review (BICR) of pathology, imaging, and oncology review data).

As of 31 August 2022, enrollment in Cohorts B1 and B2 was closed by the sponsor for business strategy reasons. This decision was not made due to any safety concerns, new emerging data, or regulatory interaction. Due to the decision to close enrollment in Cohorts B1 and B2, the Cohort B1 and B2 study objectives are no longer required.

As of 17 June 2024, the Protocol Amendment 5 revised the Cohort A study analysis plan for the primary and key secondary objectives. The rationale for this change is based on the observation from pooled treatment groups that EFS events are accumulating at a much slower rate than originally projected, together with an increasing rate of participants dropping out from EFS observation. The IA2 will be removed, and the FA for EFS based on a calendar-based data cut-off date will be conducted. Randomization to Cohort A was completed on 16 November 2021 and the EFS FA data cut-off date will be set to allow for approximately 3 years of follow-up after the last participant was randomized. The treatment period was completed on 16 November 2023. Based on the blinded observed EFS events accrual rate and assuming equal event rate across three arms, approximately 261 EFS events are expected to have occurred across all three arms (approximately 174 events for each two-arm comparison) by the EFS FA data cut-off date.

Data for Cohorts B1 and B2 will be reported at the time of PCD for Cohort A.

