**Figure 3. Testing Strategy**

The power for EFS is estimated based on the following assumptions:

- median EFS for participants receiving BCG (induction and maintenance) is 24 months.
- treatment with PF-06801591 in combination with BCG (induction and maintenance) or BCG (induction only) is expected to increase the median EFS to 34.8 months, corresponding to a HR of 0.69 under the exponential model assumption.
- 20% drop-out rate for EFS within each arm.
- non-uniform participant accrual over 22 months.

- follow-up of approximately 33 months after the last participant is randomized.

For the primary endpoint, if the true HR is 0.69, 174 EFS events in Arm A and Arm C combined will provide 68.7% power to detect a difference using a 1-sided log-rank test at a significance level of 0.025.

Based on PA5, the FA for OS will be performed at the end of the study, which is approximately 5 years after the last participant has been randomized in Cohort A. Approximately 150 OS events are expected to have occurred across the three study arms assuming equal event rate across three arms (approximately 100 OS events for each two-arm comparison) by the OS FA data cut-off date.

If the primary objective is met, a gatekeeping approach will be used to allow further testing of the key secondary endpoints of EFS for Arm B vs. Arm C, OS for Arm A vs Arm C, and OS for Arm B vs Arm C as shown in [Figure 3](#).

- For the key secondary endpoint of EFS for Arm B vs Arm C ( $H_{02}$ ), if the true HR is 0.69 under the alternative hypothesis, 174 EFS events will provide 67.4% power to detect a difference using a 1-sided log-rank test at a significance level of 0.023.
- If both  $H_{01}$  and  $H_{02}$  are rejected, 100 OS events for Arm A vs C will provide 96.3% power to detect a HR of 0.472 using a 1-sided log-rank test at the 0.025 significance level and a 2-look group sequential design with Haybittle-Peto  $\alpha$ -spending function to determine the efficacy boundary. The hazard ratio of 0.472 corresponds to an increase in the 5-year Kaplan-Meier rate for OS from 0.80^13 in Arm C to 0.90 in Arm A, under the exponential model assumption.

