      - MMM < Month of min [max(Event date + 1 day, last dose of study treatment + 1 day), end date of new anti-cancer therapy]
    - THEN
      - imputed start date = DAY (Last day of MMM) MMM YYYY ;
    - ELSE IF
      - YYYY = Year of min [max(Event date + 1, last dose of study treatment + 1), end date of new anti-cancer therapy], AND
      - MMM = Month of min [max(Event date + 1 day, last dose of study treatment + 1 day), end date of new anti-cancer therapy]

THEN

imputed start date = min [max(Event date + 1 day, last dose of study treatment + 1 day), end date of new anti-cancer therapy]);

ELSE IF

YYYY = Year of min [max(Event date + 1, last dose of study treatment + 1), end date of new anti-cancer therapy], AND

MMM > Month of min [max(Event date + 1 day, last dose of study treatment + 1 day), end date of new anti-cancer therapy]

THEN

imputed start date = 01 MMM YYYY;

ELSE IF

YYYY < Year of min [max(Event date + 1, last dose of study treatment + 1), end date of new anti-cancer therapy]

THEN

imputed start date = DAY (Last day of MMM) MMM YYYY;

ELSE IF

YYYY > Year of min [max(Event date + 1, last dose of study treatment + 1), end date of new anti-cancer therapy]

THEN

imputed start date = 01 MMM YYYY.

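### SAP 5.3.2.2 can impute a last-dose date that is too late: a known month in an earlier year becomes the EOT or death date, and a fully missing Cohort A date can become the analysis cut-off

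*SAP*

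**What the plan says.** SAP 5.3.2.2 (Exposure) gives these rules for an unknown or partly unknown last-dose date:

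- Completely missing, and neither an EOT page nor a date of death exists: "the participant should be considered to be ongoing and use the cutoff date for the analysis as the last dosing date".
- EOT page or death date available, only the year known: 31 December of that year, "if only Year is available and Year < Year of min (EOT date, death date").
- EOT page or death date available, year and month known: "Last day of the month, if both Year and Month are available and Year = Year of min (EOT date, death date") and the month is earlier.
- Anything else with an EOT page or death date: "min (EOT date, death date), for all other cases".

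The comparable algorithm for the start of new anti-cancer therapy (SAP 5.3.3.4) has a separate branch for a known month in an earlier year: "imputed start date = DAY (Last day of MMM) MMM YYYY".

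On timing, SAP 2 says of Cohort A: "The treatment period was completed on 16 November 2023". It also says that the "EFS FA data cut-off date will be set to allow for approximately 3 years of follow-up after the last participant was randomized", and randomization ended on 16 November 2021. The power assumptions in SAP 5.1.1 use a shorter period: "follow-up of approximately 33 months after the last participant is randomized".

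**The concern.** The rules in 5.3.2.2 are meant to keep whatever part of the date was recorded. In one configuration they discard it: a recorded year and month in an earlier calendar year is overwritten by a later date that the record excludes. The rule for a completely missing date assumes that the participant may still be on treatment. That cannot be so for Cohort A at an EFS cut-off that falls after treatment was completed.

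Last dose is an anchor for several safety outputs: duration of exposure (SAP 6.5.3.1), the on-treatment window of last dose plus 30 days (3.5.1 and 5.2.7), the irAE window of last dose plus 90 days (Appendix 1), and deaths within 30 days of last dose (6.6.2). A date that is too late lengthens exposure and can move off-treatment events inside these windows.

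**Working it through.** No sample size, power or alpha figure depends on these rules, so there is no stated number to reproduce. The check applies the rules literally and then does calendar arithmetic. The participant dates below are illustrative, not trial data.

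**1. Known month in an earlier year**

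Let R = min(EOT, death). The year-only branch does not apply because the month is known. The month branch does not apply because it requires the recorded year to equal the year of R. The date therefore falls to the residual rule and becomes R.

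Overstatement = R − last day of the recorded month. This is a minimum, because month end is the latest date that the record allows.

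| Recorded last dose | R | SAP result | Month end | Overstatement |
|---|---|---|---|---|
| Dec 2022 | EOT 4 Jan 2023 | 4 Jan 2023 | 31 Dec 2022 | 4 days |
| Nov 2022 | EOT 10 Jan 2023 | 10 Jan 2023 | 30 Nov 2022 | 31 + 10 = 41 days |
| Nov 2022 | EOT 20 Mar 2023 | 20 Mar 2023 | 30 Nov 2022 | 31 + 31 + 28 + 20 = 110 days |
| Mar 2022 | death 15 Feb 2023, no EOT page | 15 Feb 2023 | 31 Mar 2022 | 321 days |
| Mar 2023 | EOT 10 Jun 2023 | 31 Mar 2023 | 31 Mar 2023 | 0 days |

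The last row shows that the same-year case works. Two comparisons suggest that the gap is an omission:

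- With EOT on 20 March 2023, a record of 2022 alone becomes 31 December 2022, while a record of November 2022 becomes 20 March 2023. More information gives a later and contradictory date.
- SAP 5.3.3.4 includes the corresponding earlier-year branch.

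In the fourth row the imputed last dose is the death date, so that death is automatically counted among deaths within 30 days.

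**2. Completely missing date, no EOT page, no death date**

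Cohort A treatment ended on 16 November 2023. The EFS cut-off can be read in two ways:

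- 16 November 2021 + 3 years = 16 November 2024. The gap from treatment end is 366 days; 366 / 30.4375 = 12.0 months.
- 16 November 2021 + 33 months = 16 August 2024. The gap is 274 days; 274 / 30.4375 = 9.0 months.

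Under the 3-year reading, an affected TEAE window would nominally run to 16 December 2024 instead of 16 December 2023 at the latest. The irAE window would run to 14 February 2025 instead of 14 February 2024. Both are cut short in practice because data after the cut-off are not used (SAP 5.2.1).

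**3. Cohorts B1 and B2**

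SAP 5.3.2.2 is not restricted to Cohort A. Enrollment to B1 and B2 closed on 31 August 2022. Cycle 25 Day 1 in B1 is 24 × 28 = 672 days after first dose, and Cycle 17 Day 1 in B2 is 16 × 42 = 672 days after. A participant starting on the closing date would reach either on about 3 July 2024, which is after 16 November 2023.

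**The case against.** The best case for leaving the rules alone is that they will rarely bite, and then weakly.

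- The Cohort A schedule of activities places the EOT visit within 7 days of the later drug's last dose, or of the decision to stop both. When it follows the last dose on time, a year crossing means late December to early January, an error of days. This stands for most cases. It fails when only a death date exists, or when the decision to stop comes long after the last dose. In BCG-only Arm C the planned gap between maintenance courses from Cycle 7 is 154 days (SAP 6.5.3.4).
- In Arms A and B, the last dose of study treatment is the later of the two drugs' dates (SAP 3.4.1). A wrong date for one drug then matters for the windows only if it becomes the later one. This stands, although that drug's own exposure would still be overstated.
- Every Cohort A participant should have an EOT visit, so the cut-off rule should seldom fire. When it does, few extra events may be captured: active AE collection is required for a minimum of 90 days after last dose (Protocol 8.3.1), and the schedule of activities limits later reporting to treatment-related SAEs. The TEAE window also stops at new anti-cancer drug therapy; the irAE window does not.

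A reader might infer more than the documents support:

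- *Every known earlier month is overwritten.* It is not; same-year months go to month end.
- *The cut-off rule also misclassifies deaths.* It cannot, because it requires that there is no death date.
- *The overstatement reaches about 36 months at the OS final analysis.* That would need the safety outputs to be rerun then, which SAP 5.1.2 and 7 do not state.
- *The primary result is affected.* The primary EFS event and censoring rules (SAP Table 11) do not use last dose. Last dose enters only the imputation of an incomplete start date for new anti-cancer therapy, which is used for censoring in one EFS sensitivity analysis.

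**Conclusion.** The point holds as two narrow errors in SAP 5.3.2.2.

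The missing earlier-year branch is a rule that yields a date the record contradicts. The overstatement is 4 to 321 days in the examples, and usually days when EOT is on time. The cut-off rule conflicts with the SAP's own statement that Cohort A treatment had ended, by about 9 months on the 33-month reading and about 12 months on the 3-year reading.

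For affected participants both errors overstate exposure and lengthen the TEAE and irAE windows. Only the first can also move a death into the 30-day category. It does not follow that on-treatment windows are wrong across the study: only participants with an incomplete last-dose date are exposed to either error. The documents give no count, and I assume that it is small. This is a minor correction with no bearing on alpha, power or the primary analysis.

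**What to change.** In SAP 5.3.2.2:

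1. Add a branch: if year and month are available and the year is earlier than the year of min(EOT, death), use the last day of that month.
2. For Cohort A, when the date is completely missing with no EOT page and no death date, replace the cut-off with the last recorded non-zero dose date of that drug, in any case no later than 16 November 2023. A recorded dose after that day should be queried.
3. Do not apply the 16 November 2023 limit to Cohorts B1 and B2. Their planned dosing could run to about 3 July 2024, and the limit could cut genuine exposure.

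While the section is open, add a rule for a partial date with no EOT page and no death date, which currently has none.

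The cost is a few lines in the SAP and matching lines in the derivation program. Counting the participants who reach each branch before database release would show whether any table changes.

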### 5.3.3. Imputation rules for date of last contact and efficacy assessments

#### 5.3.3.1. Date of last contact

The date of last contact will be derived for participants not known to have died at the analysis cut-off using the latest complete date (non-imputed) among the following:

- All participant assessment dates (blood draws [laboratory, PK], vital signs, performance status, ECG, disease assessments, radiation, surgery)
- Start and end dates of anti-cancer therapies
- Start and stop dates of concomitant therapies including non-drug treatments or procedures
- Completion dates for PRO Questionnaires
- AE start and end dates
- Study drug start and end dates
- Randomization date
- Withdrawal of consent date
- Last date of contact where “Subject Remains in Follow-up” or “Subject No Longer Being Followed for Survival” collected on the “Survival Follow-up” eCRF
- Date of discontinuation on disposition eCRF pages (do not use if reason for discontinuation is lost to follow-up or death).

Only dates associated with actual examinations of the participant will be used in the derivation. Dates associated with a technical operation unrelated to participant status such as the date a blood sample was processed will not be used. Assessment dates after the cut-off date will not be applied to derive the last contact date.

### 5.3.3.2. Death date

If there is a record for death, but the date is missing or is partial, it will be imputed based on the last contact date.

- If the date is missing, the death date will be imputed as the day after the date of last contact.
- If the day or both day and month is missing, the death date will be imputed to the maximum of the full (non-imputed) day after the date of last contact and the following:
  - 1st day of the month and year of death, if day of death is missing, OR
  - January 1st of the year of death, if both the day and month of death are missing.

### 5.3.3.3. Disease assessments

All investigation dates (e.g., cytology, cystoscopy, biopsy, CT/MRI/urogram scan) must be completed with day, month, and year.

If there are multiple disease assessment dates associated with an evaluation, i.e., if cytology, cystoscopy, biopsy, CT/MRI/urogram scan assessments occur over a series of days rather than the same day, the choice of date of assessment could impact the date of EFS event and/or date of complete response. If there are multiple assessment dates associated with an evaluation, the earliest of the assessment dates associated with the evaluation will be used as the date of assessment.

If one or more investigation dates for an evaluation are incomplete but other investigation dates are available, the incomplete date(s) are not considered for calculation of the assessment date and assessment date is calculated as the earliest of all investigation dates (e.g., cytology, cystoscopy, biopsy, or CT/MRI/urogram scan).

If all assessment dates for an evaluation have no day recorded, the 1st of the month is used.

If the month is not completed, for any of the investigations for an evaluation, the respective assessment will be considered to be at the date which is exactly between the previous and the following assessment. If both a previous and following assessments are not available, this assessment will not be used for any calculations.

### 5.3.3.4. Date of start of new anti-cancer therapy

Incomplete dates for start date of new anti-cancer therapy will be imputed as follows and may be used for determining censoring dates for efficacy analyses. Event date below refers to progression of disease, recurrence of high-grade disease or persistence of CIS date by investigator assessment. If the imputation results in an end date prior to the imputed start date, then the imputed start date should be set to the end date.

- The end date of new anti-cancer therapy will be included in the imputations for start date of new anti-cancer therapy. If the end date of new anti-cancer therapy is
  - completely missing then it will be ignored in the imputations below

- partially missing with only year (YYYY) available then the imputations below will consider 31DECYYYY as the end date of the new anti-cancer therapy
- partially missing with only month and year available then the imputations below will consider the last day of the month for MMMYYYY as the end date of the new anti-cancer therapy

- For participants who have not discontinued study treatment at the analysis cut-off date, last dose of study treatment is set to the analysis cut-off date in the imputations below.
- If the start date of new anti-cancer therapy is completely or partially missing, then the imputed start date of new anti-cancer therapy is derived as follows:
  - Start date of new anti-cancer therapy is completely missing
    - Imputed start date = min [max(Event date + 1, last dose of study treatment + 1), end date of new anti-cancer therapy]
  - Only year (YYYY) for start of anti-cancer therapy is available
    - IF YYYY < Year of min [max(Event date + 1, last dose of study treatment + 1), end date of new anti-cancer therapy] THEN imputed start date = 31DECYYYY;
    - ELSE IF YYYY = Year of min [max(Event date + 1, last dose of study treatment + 1), end date of new anti-cancer therapy]
    - THEN imputed start date = min [max(Event date + 1, last dose of study treatment + 1), end date of new anti-cancer therapy]
    - ELSE IF YYYY > Year of min [max(Event date + 1, last dose of study treatment + 1), end date of new anti-cancer therapy]
    - THEN imputed start date = 01JANYYYY
  - Both Year (YYYY) and Month (MMM) for start of anti-cancer therapy are available
    - IF
      - YYYY = Year of min [max(Event date + 1, last dose of study treatment + 1), end date of new anti-cancer therapy], AND
      - MMM < Month of min [max(Event date + 1 day, last dose of study treatment + 1 day), end date of new anti-cancer therapy]
    - THEN
      - imputed start date = DAY (Last day of MMM) MMM YYYY ;
    - ELSE IF
      - YYYY = Year of min [max(Event date + 1, last dose of study treatment + 1), end date of new anti-cancer therapy], AND
      - MMM = Month of min [max(Event date + 1 day, last dose of study treatment + 1 day), end date of new anti-cancer therapy]

THEN

imputed start date = min [max(Event date + 1 day, last dose of study treatment + 1 day), end date of new anti-cancer therapy]);

ELSE IF

YYYY = Year of min [max(Event date + 1, last dose of study treatment + 1), end date of new anti-cancer therapy], AND

MMM > Month of min [max(Event date + 1 day, last dose of study treatment + 1 day), end date of new anti-cancer therapy]

THEN

imputed start date = 01 MMM YYYY;

ELSE IF

YYYY < Year of min [max(Event date + 1, last dose of study treatment + 1), end date of new anti-cancer therapy]

THEN

imputed start date = DAY (Last day of MMM) MMM YYYY;

ELSE IF

YYYY > Year of min [max(Event date + 1, last dose of study treatment + 1), end date of new anti-cancer therapy]

THEN

imputed start date = 01 MMM YYYY.

#### 5.3.4. Other Missing or Partial Dates

Imputation methods generally apply to partial dates as follows:

- If the day of the month is missing for a start date used in a calculation, the 1st of the month will be used to replace the missing date.
- If both the day and month are missing, the first day of the year is used.
- For stop dates, the last day of the month, or last day of the year is used if the day or day and month are missing, respectively.

These rules are used unless the calculations result in negative time durations (e.g., date of resolution cannot be prior to date of onset). In this case, the resolution and onset dates will be the same and the duration will be set to 1 day.

## 6. ANALYSES AND SUMMARIES

Refer to [Section 4](#) for definitions of analysis sets and [Section 5.2](#) for general methodology.

For Cohort A, analyses and summaries will be by treatment arm.

Cohorts B1 and B2 will be reported separately from Cohort A.

### 6.1. Primary Endpoint(s)

#### 6.1.1. Event-free survival as assessed by investigator (Cohort A only)

##### 6.1.1.1. Primary analysis (for Arm A vs Arm C)

Refer to [Section 2.2.1](#) for the primary estimand.

In this study, disease may be assessed through cytology, cystoscopy, biopsy, and imaging scans conducted at screening (required), every 12 weeks for 2 years following randomization, and every 24 weeks thereafter until first occurrence of progression of disease, recurrence of high-grade disease, or persistence of CIS (for participants with CIS at baseline) regardless of initiation of subsequent anti-cancer therapy.

EFS is defined as the time from randomization until progression of disease, recurrence of high-grade disease, persistence of CIS, or death due to any cause, whichever occurs first.

An event is as defined in Table 10. The censoring and event date options to be considered for the EFS analysis ([Section 2.2.1](#)) are presented in Table 11.

$$\text{EFS (months)} = [\text{date of event or censoring} - \text{date of randomization} + 1]/30.4375$$

